50 individuals with trichotillomania or skin picking disorder will be recruited for a double-blind, placebo-controlled pilot study in which dronabinol or placebo is administered in a 1:1 fashion. All 50 subjects will have trichotillomania or skin picking disorder per DSM-5 criteria. Following baseline measures, all subjects will be randomized to either dronabinol or placebo and seen every 2 weeks for the first four weeks and every 3 weeks for the remainder of the 10-week period.

Participants will be started at 5mg po qday for 2 weeks, then 5mg po bid for 2 weeks and then 5mg TID for the remaining 6 weeks. Participants will only go up to the full dose if clinically needed. Efficacy and safety measures will be performed at each visit.

The study will be conducted in accordance with the International Conference on Harmonization Guideline for Good Clinical Practice, all local ethical and legal requirements, and the World Medical Assembly (Declaration of Helsinki). The study protocol and procedures will be approved by the University of Chicago's institutional review board prior to any recruitment. Written informed consent will be required for study participation.

Randomization of drug will be conducted in blocks of eight. The blind will be assessable to the study subject at all times by calling the pharmacy number listed on the medication bottle. The investigational pharmacy will follow proper accountability procedures in regards to both randomization of the study drug and holding of the blind.

Subjects:

Inclusion criteria:

- 1) men and women age 18-65;
- 2) current DSM-5 trichotillomania or skin picking disorder; and
- 3) Ability to understand and sign the consent form.

Exclusion criteria:

- 1) Unstable medical illness based on history or clinically significant abnormalities on baseline physical examination
- 2) Current pregnancy or lactation, or inadequate contraception in women of childbearing potential
- 3) Subjects considered an immediate suicide risk based on the Columbia Suicide Severity rating Scale (C-SSRS) (www.cssrs.columbia.edu/docs)
- 4) Past 12-month DSM-5 diagnosis of psychosis, major depressive disorder, bipolar disorder, mania, or a substance or alcohol use disorder
- 5) Illegal substance use based on urine toxicology screening
- 6) Stable dose of medications for at least the past 3 months
- 7) Previous treatment with dronabinol

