- Rapid Visual Processing Task (RVP)
- Spatial Working Memory Task (SWM)
- Cambridge Gambling Task (CGT)

Following-Up Visit Assessments

All follow-up visits will include all psychiatric measures (except the MINI which will be done at baseline only) and safety measures (adverse events, vital signs, C-SSRS). There will be four follow up visits for a total of five visits.

Subject Compensation

Subjects will be compensated \$20 per visit, for a total of \$100. Compensation will be given in the form of a check at the end of the study, as per University of Chicago protocol.

Safety Assessments

Safety and tolerability will be assessed using spontaneously reported adverse events data, Columbia–Suicide Severity Rating Scale (C-SSRS), vital signs, and by evaluating premature termination. Safety assessments (C-SSRS, sitting blood pressure, heart rate, adverse effects, and concomitant medications) will be documented at each visit. Subjects who are an immediate suicide risk will be removed from the study and appropriate clinical intervention (e.g. hospitalization) will be arranged. Urine pregnancy tests will be performed at the initial visit. Subjects who have a positive urine pregnancy test will be excluded from the study. Assessment of side effects will be done at each visit. AEs will be coded by system organ class (SOC) and preferred term (PT) using the Medical Dictionary for Regulatory Activities (Med- DRA) Version 11.1. The incidences of all AEs will be summarized descriptively. In terms of vital signs, those subjects with abnormal blood pressures will be assessed for symptoms of hypo- or hypertension. Asymptomatic subjects will be evaluated each visit for changes in vital signs. In the case of hypertensive emergencies (BP greater than 210/120), appropriate referral to the emergency room will be made. In the case of hypotension (BP less than 90/60), participants will be evaluated for symptoms of hypotension and if symptomatic, appropriate interventions will be made.

Seizure and seizure-like activity have been reported in patients receiving dronabinol. Therefore, history of seizures will be an exclusion criterion. If a seizure occurs, dronabinol will be discontinued. Participants will be advised to discontinue dronabinol and contact a healthcare provider immediately if they experience a seizure.

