Although the seizure risk needs to be taken seriously, the occurrence of new seizures from dronabinol, when excluding patients with a seizure disorder, appears to be fairly low even in medically compromised patient (25). In the proposed study, our dose of dronabinol is only up to a total of 15mg each day and patients with trichotillomania are on average quite healthy. This may explain why we saw only a small amount of mild side effects in our previous study (4).

Table 1 outlines adverse events that occurred in subjects with AIDS –related anorexia and chemotherapy-related nausea as well as not medically compromised subjects with trichotillomania (4).

Table 1
Adverse events associated with dronabinol

Adverse event	Pooled trial data from studies of subjects with AIDS-related anorexia and chemotherapy-related nausea ^a	Trichotillomania study participants (n = 14)			
		2.5 mg/day (n = 14)	5 mg/day (n = 13)	10 mg/day (n = 12)	15 mg/day (n = 7)
Light-headed/dizzy	3–10%	2 (14.3%)	1 (7.7%)	1 (8.3%)	–
“High” (i.e., easy laughing, elation, and heightened awareness)	8–24%	–	1 (7.7%)	2 (16.7%)	–
Sedation	3–10%	1 (7.7%)	1 (7.7%)	–	–
Dry mouth	Frequency not specified	–	1 (7.7%)	1 (7.7%)	–
Constipation	Frequency not specified	–	1 (7.7%)	–	–
Headache	<1%	–	–	1 (7.7%)	–
Nausea/vomiting	3–10%	–	1 (7.7%)	–	–
Abdominal pain	3–10%	–	–	–	–
Paranoia	3–10%	–	–	–	–

	Pooled trial data from studies of subjects with AIDS-related anorexia and chemotherapy-related nausea ^a	Trichotillomania study participants (n = 14)			
Any side effect	Frequency not specified	3 (21.4%)	6 (46.2%)	5 (41.7%)	0

^a <http://www.fda.gov/ohrms/dockets/dockets/05n0479/05N-0479-emc0004-04.pdf>

and <http://www.merckmanuals.com/professional/lexicomp/dronabinol.html>

Subject Withdrawal

If a subject withdraws from the study, all instruments administered at the screening visit will be completed at the final visit. These will be conducted when the subject is able to come in for an early termination visit. Withdrawn subjects will be given the phone number of the principal investigator as well as the phone numbers of local resources for trichotillomania and skin picking.

Data and Safety Monitoring Plan

1. Responsibility for Data and Safety Monitoring

The PI will have overall responsibility for monitoring the integrity of study data and participant safety.

2. Procedures for Monitoring Participant Safety

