- Any moderate adverse event which appears definitely, probably, or possibly related to study participation will be reported to the University of Chicago IRB in writing within 20 working days.
- Any mild adverse event will be summarized in the IRB annual progress reports.

Statistical Analysis

Design/Randomization

The study is a double-blind, placebo-controlled study. Participants will be randomized (1:1) to receive dronabinol or placebo by the University of Chicago Investigational pharmacy in block sizes of eight, using computer-generated randomization with no clinical information.

Due to the pandemic of COVID19, study participants can perform their baseline and follow-up visits online using encrypted Zoom instead of in person visits. All inventories will be assessed. Blood samples and urine toxicology, however, will be at the discretion of the study PI. In cases where they are considered medically necessary, the participant can have them drawn locally and submitted to the study team.

Efficacy Analysis

For statistical analysis, the full-analysis set will be defined as all participants who took at least 1 dose of the study drug and had at least 1 post-randomization primary efficacy assessment. The safety-analysis set will be defined as all randomized participants who took at least 1 dose of the study drug and completed at least 1 post-randomization safety assessment. Participants with trichotillomania and skin picking disorder will be grouped as one BFRB group.

We will compare the baseline characteristics of both groups using Fisher's exact test for categorical variables and the t test for continuous variables. We will calculate adherence to treatment, based on the number of pills returned at each visit, as the number of pills taken divided by the number of days in the study $\times 100\%$.

Primary endpoint analysis

The primary outcome measure will be the change from first randomization visit to study endpoint in total composite score on the NIMH Trichotillomania Symptom Severity Scale(s) and the Sheehan Disability Scale.

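### The safety-analysis set requires a completed post-randomization assessment, so it may drop dosed participants who leave before one, including any with a known adverse event

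*Combined protocol and SAP*

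**What the plan says.** The Efficacy Analysis section sets three conditions for the safety-analysis set: randomization, at least one dose, and a later completed assessment. In full, it is "all randomized participants who took at least 1 dose of the study drug and completed at least 1 post-randomization safety assessment".

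Other sections bear on the third condition:

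- **Timing (Methodology).** Participants are "seen every 2 weeks for the first four weeks and every 3 weeks for the remainder of the 10-week period". Follow-up visits therefore fall at weeks 2, 4, 7 and 10.
- **Content (Safety Assessments).** "Safety assessments (C-SSRS, sitting blood pressure, heart rate, adverse effects, and concomitant medications) will be documented at each visit".
- **Data sources (Safety Assessments).** "Safety and tolerability will be assessed using spontaneously reported adverse events data". The same sentence goes on to name the C-SSRS, vital signs and premature termination.
- **Leaving early (Subject Withdrawal).** Withdrawn participants are to complete the screening-visit instruments. "These will be conducted when the subject is able to come in for an early termination visit".
- **Remote visits (Design/Randomization).** Because of the pandemic, "study participants can perform their baseline and follow-up visits online using encrypted Zoom instead of in person visits".
- **Test (Safety analyses).** Treatment-emergent adverse events are compared between arms by Fisher's exact test. No analysis set is named there, and the safety-analysis set is the only one defined for safety.

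No section says how to handle a dosed participant who is never assessed afterwards, or an event reported between visits before week 2.

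**The concern.** A safety population is normally fixed by exposure. Here it also depends on something that happens after exposure and may be affected by it. A participant could take the drug, have an adverse effect, tell the study team, stop and not return. The Safety Assessments section treats both the report and the early stop as tolerability information, but the set definition, read as written, may leave that person out of numerator and denominator alike.

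Safety is part of the primary aim, and the arms are small. One person is 4% of an arm of 25, so even one or two exclusions can visibly move an incidence or a discontinuation rate.

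**Working it through.** The plan attaches no figure to this definition, so there is none to reproduce. The check has two parts.

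**1. Can a dosed participant fall outside the set?**

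- The assessments are listed as visit-based, and the first follow-up visit is at week 2. That leaves two weeks of dosing before any scheduled assessment.
- The withdrawal visit narrows the gap but does not close it, because it depends on attendance. The Subject Withdrawal section also asks only for the screening-visit instruments, and the list under Baseline Assessments names neither adverse events nor the C-SSRS. The rule that safety is documented at each visit may still cover such a visit.
- Online visits make an assessment easier to obtain, but do not guarantee one.
- Nothing elsewhere returns an unassessed participant to the set.

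So exclusion is possible under the text, but its frequency is not stated.

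**2. What would it do to the incidence?**

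Inputs:

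- *Arm size, n = 25.* The Methodology section says "50 individuals with trichotillomania or skin picking disorder will be recruited for a double-blind, placebo-controlled pilot study", and Design/Randomization says "Participants will be randomized (1:1) to receive dronabinol or placebo"; 50/2 = 25. (The Sample Size section speaks of 50 in each group; the recruitment total is used here.)
- *Dronabinol incidence, 40% to 48% (assumed).* Table 1 reports any side effect in 6/13 (46.2%) at 5 mg/day and 5/12 (41.7%) at 10 mg/day in the sponsor's open-label study. The table also shows 3/14 (21.4%) at 2.5 mg/day and none of 7 at 15 mg/day, so the range is only a working assumption.
- *Early leavers never assessed, k (assumed).* Taken as 0 to 3 in the dronabinol arm.

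Let x be the number with a known event among the n dosed, and e the number with a known event among the k leavers.

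- All-dosed set: x / n
- Set as written: (x − e) / (n − k)

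The written rule lowers the incidence when e/k exceeds x/n and raises it when e/k is below x/n.

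*Every leaver had a known event (e = k):*

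| All dosed | k = 1 | k = 2 | k = 3 |
|---|---|---|---|
| 10/25 = 40.0% | 9/24 = 37.5% | 8/23 = 34.8% | 7/22 = 31.8% |
| 11/25 = 44.0% | 10/24 = 41.7% | 9/23 = 39.1% | 8/22 = 36.4% |
| 12/25 = 48.0% | 11/24 = 45.8% | 10/23 = 43.5% | 9/22 = 40.9% |

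Each exclusion lowers the incidence by about 2 to 3 points, and three exclusions lower it by 7 to 8 points.

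*No leaver had an event (e = 0):* 11/25 = 44.0% becomes 11/24 = 45.8% for k = 1 and 11/23 = 47.8% for k = 2. The incidence rises.

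*Leavers had events that nobody reported:* suppose 11 of 25 truly had an event and two of them left without reporting it. The written rule gives 9/23 = 39.1%. An all-dosed set counts the two as non-events and gives 9/25 = 36.0%, which is further from 44.0%.

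*Discontinuations:* if the k leavers were the only discontinuations for adverse events, and that summary used the safety-analysis set, the rate would go from k/25 (4% for one, 8% for two) to 0/(25 − k) = 0.

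The same arithmetic applies to losses from placebo, where it moves the between-arm difference the other way.

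**The case against.** The strongest reply is that the effect may be nil. The Sample Size section expects few drop-outs, follow-up may be online, and a withdrawal visit is planned. This stands, and it limits the weight of the point.

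Second, the term safety assessment is not defined for the set. Since the Safety Assessments section says safety is assessed from spontaneous reports, a phoned-in report might itself qualify. This also stands in part. The visit-based list supports the stricter reading, so the text is ambiguous and needs settling.

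Third, the protocol says all adverse events will be summarized descriptively without naming a set, and the Fisher test names none. Adverse-event reporting to the IRB, and of serious events to the monitoring committee, also does not depend on the set. Known events are therefore not lost to oversight. That does not place them in the between-arm comparison, for which the safety-analysis set is the natural population.

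A reader might go further and infer that the rule removes mainly people who left because of adverse effects on active drug, and so flatters dronabinol. The documents do not support this: they give no drop-out rate, overall or by arm, and no reasons for leaving before week 2.

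A reader might also infer that the rule would overturn a significance result. Assume zero placebo events and two dronabinol leavers with events. By two-sided Fisher's exact test, 6/25 vs 0/25 (p = 0.022) becomes 4/23 vs 0/25 (p = 0.046), still below 0.05. Likewise 5/25 vs 0/25 (p = 0.0502) becomes 3/23 vs 0/25 (p = 0.102), above 0.05 both times. With an assumed 11/25 vs 3/25 (p = 0.026), losing two gives p = 0.046, and only losing three takes it above 0.05 (p = 0.083). These are constructed cases and do not show a changed conclusion.

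**Conclusion.** The point holds as a possible selection effect in an outcome that belongs to the primary aim. The definition conditions on a post-treatment event, and no other section restores dosed participants who are never assessed.

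The size is uncertain and may be zero. Assuming 25 per arm, a dronabinol incidence of 40% to 48%, and leavers with known events, the cost is roughly 2 to 3 percentage points of observed incidence per excluded dronabinol participant. The result looks more favourable to dronabinol only when known events are more frequent among its excluded leavers than in the arm as a whole; event-free leavers push it the other way. The change is worth making because it costs little and removes an avoidable ambiguity, not because a bias has been shown.

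**What to change.** Before unblinding, amend the definition and add short rules:

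1. The safety-analysis set is every randomized participant who took at least one dose, analysed by treatment received.
2. Adverse events and discontinuations count whatever the route of report, whether or not a scheduled assessment was completed.
3. The number of dosed participants with no post-dose assessment is reported by arm, with the reason for leaving where known.
4. The report states that unreported events in these participants count as non-events, so the incidence may be understated.
5. The Safety analyses section names this set for the Fisher test and for the summary of premature termination.

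The cost is a few sentences of text and slightly more reporting, with no new data collection. The one real drawback is item 4: where a leaver's event was never reported, the all-dosed denominator gives a slightly lower rate than the present rule. Item 3 makes that visible. If nobody is lost before assessment, the results do not change.

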Given the serious personal consequences associated with trichotillomania and skin picking disorder, and the likelihood of success of dronabinol in treating both disorders, the aim of the present study was to examine the efficacy and safety of dronabinol vs placebo in adults with trichotillomania or skin picking disorder using a double-blind, placebo-controlled design.

We hypothesize that dronabinol will be more effective than placebo in reducing the frequency of hair pulling and skin picking and in improving overall psychosocial functioning after 10 weeks of treatment when compared to baseline.

Primary Aim/Objective

The aim of the present study is to examine the efficacy and safety of dronabinol vs placebo in adults with trichotillomania and skin picking disorder.

Co-Primary Endpoint(s):

The co-primary efficacy measures will be the change in hair pulling or skin picking frequency and urges to pull hair or pick skin for the past week as indicated by change in total score on the *NIMH Trichotillomania Symptom Severity Scale* (for TTM) or *Skin Picking Symptom Assessment Scale* (for SPD), reliable and valid clinician-administered measures (18-19), as well as the same scale modified for skin picking disorder, and the change in psychosocial functioning over the same time period using the *Sheehan Disability Scale* (20). The co-primary efficacy end points will be the change in these measures from baseline to week 10.

Secondary Aim/Objective

A secondary aim of the study is to examine the effects of dronabinol vs placebo on self-report measures of hair pulling, skin picking, quality of life, and measures of mood and anxiety.

Secondary Endpoint(s):

Secondary efficacy measures include the change in number of days per week pulling, the *Clinical Global Impressions–Improvement Scale* (CGI-I) rated global improvement of symptoms over time (results will be dichotomized as improved [CGI-I ratings of 1 or 2 very much/much improved] or not improved [CGI-I ratings of 3-7]) (20), the self-report *Massachusetts General Hospital Hairpulling Scale* (22), the *Skin Picking Symptom Assessment Scale*, the *Quality of Life Inventory* (23), the *Hamilton Depression Rating Scale* (24), the *Hamilton Anxiety Rating Scale* (25), and the *Tridimensional Personality Questionnaire*

Methodology

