- 8) Cognitive impairment that interferes with the capacity to understand and self-administer medication or provide written informed consent

Baseline Assessments:

Those subjects who appear appropriate for the study, based on telephone screening, will be invited for a baseline assessment. The duration of the baseline assessment will be approximately 90 minutes and will include the following: informed consent, demographic data, concomitant medications (no psychotropic medications will be allowed), and family history data. There will also be a physical examination (including weight, and vital signs, urine pregnancy test for women of childbearing years and urine drug screen, as well as a baseline blood draw to assess nutritional status. The blood draw is optional to the subject and will administered at the PI's discretion). Finally, the subjects will undergo a psychiatric evaluation (using the MINI International Neuropsychiatric Interview).

In addition, the following instruments will be completed at the screening visit: 1) NIMH Trichotillomania Symptom Severity Scale (or the same scale modified for skin picking); 2) Sheehan Disability Scale; 3) Massachusetts General Hospital Hairpulling Scale; 4) the 17-item

Hamilton Rating Scale for Depression (HAM-D); 5) the 17-item Hamilton Rating Scale for Anxiety (HAM-A); 6) Clinical Global Impression (Improvement and Severity) scale; 7) Cambridge Caffeine Use Questionnaire; 8) The Dietary Fat and Free Sugar Questionnaire and 9) the Quality of Life Inventory; 10) Cambridge-Chicago Trait Scale (12); the Skin Picking Symptom Assessment Scale (SP-SAS); and the Body Focused Repetitive Behavior Broad Assessment Measure (BFRB-BAM), a new scale being added for validation purposes. In addition, subjects will undergo cognitive assessments at baseline and study endpoint.

Cognitive Assessments: Assessments of cognitive control will be comprised of several valid paradigms (See below). These tasks are designed to probe dissociable neural circuitry and cognitive processes likely to be implicated in the pathophysiology of addictions. Task order was chosen arbitrarily and will be applied consistently across subjects, to minimize possible confounding factors of differences in task order across participants.

The following tasks will be administered at baseline and final visits:

- Stop Signal Task of Inhibitory Control (SST)
- Intra-dimensional/Extra-dimensional Set Shift Task (ID/ED task)
- One Touch Stockings Task (OTS)

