The primary analysis of efficacy for continuous measures will be analysis of variance (ANOVA), with terms for treatment to assess differences between treatment groups in the change from first randomization visit to endpoint using the last observation carried forward. The primary analysis for global improvement and response categories will be the Cochran-Mantel-Haenszel test using the last observation carried forward. The primary analysis for $\geq 5\%$ reduction in weight will be Fisher's exact test using the last observation carried forward.

Secondary endpoints analyses

Secondary outcome measures will include the change from first randomization visit to study endpoint in CGI severity and improvement scales, self-reported hair pulling behavior using the MGH-HPS, self-reported skin picking behavior using the SP-SAS, the change in depressive and anxiety symptoms, change in quality of life, and impacts on personality markers. We will use a longitudinal analysis comparing the rate of change of the outcome during the treatment period between groups. The difference in rate of change will be estimated by random regression methods. The model for the mean of the outcome will include terms for treatment, time, and treatment-by-time interaction. To account for the correlation of observations within participants, we will use SAS procedure MIXED with a first-order antedependence covariance structure. The longitudinal analyses will use all available observations from all time points from all participants who completed a randomization visit evaluation.

Safety analyses

We will evaluate differences between groups in the incidence of treatment-emergent adverse events using Fisher's exact test. Descriptive statistics will be used to evaluate changes in laboratory values, blood pressure and heart rate.

Sample Size

The sample size was calculated for the co-primary endpoint of change from randomization. For 80% power to compare the change from randomization, assuming a true effect size of 0.5 between treatment group and the placebo group, 50 participants with a BFRB will be needed in each treatment group based on a 2-group t test at the .05 level of significance. Given the low rates of adverse events expected with dronabinol, we expect few drop-outs from the study and therefore a smaller sample is needed.

Data Management Plan

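### The symptom co-primary pools hair-pulling and skin-picking change scores with no diagnosis term and no settled common scale, which weakens its interpretation and precision but not its validity

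*Combined protocol and SAP*

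**What the plan says.** **Pooling.** Under Efficacy Analysis: "Participants with trichotillomania and skin picking disorder will be grouped as one BFRB group".

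**Model.** Under Primary endpoint analysis, the continuous measures are compared by "analysis of variance (ANOVA), with terms for treatment to assess differences between treatment groups" in change to endpoint. No diagnosis term, conversion between scales or by-diagnosis estimate is described. Design/Randomization specifies blocks of eight and makes no use of clinical data, so allocation is not stratified by diagnosis.

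**Instrument for skin picking (SPD).** The text points two ways.

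- Co-Primary Endpoint(s), first clause: "change in total score on the *NIMH Trichotillomania Symptom Severity Scale* (for TTM) or *Skin Picking Symptom Assessment Scale* (for SPD"), which assigns the SP-SAS to SPD and the NIMH scale to trichotillomania (TTM).
- The same sentence continues: "as well as the same scale modified for skin picking disorder".
- Baseline Assessments lists "NIMH Trichotillomania Symptom Severity Scale (or the same scale modified for skin picking"), with the SP-SAS as a separate entry.
- Primary endpoint analysis defines the outcome as "total composite score on the NIMH Trichotillomania Symptom Severity Scale(s) and the Sheehan Disability Scale" and does not name the SP-SAS.
- Secondary endpoints analyses lists "self-reported skin picking behavior using the SP-SAS". Secondary Endpoint(s) also lists the SP-SAS as secondary.

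**The concern.** If the first clause of the co-primary definition is followed, the analysis averages raw points from two different scales. A one-point change then need not mean the same thing in the two diagnoses, the estimate cannot be read on either scale, and the scale with the larger spread carries more than its share of the result.

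Even if SPD is scored on a modified NIMH scale, the two versions measure different behaviours. Without a diagnosis term, any difference between diagnoses in mean change goes into the residual variance. A chance difference between arms in the TTM:SPD mix then moves the estimate as well. With 25 participants per arm there is little precision to give away.

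The instrument conflict brings two further problems. The co-primary measures are described as clinician-administered, while the SP-SAS is described as self-reported. If the SP-SAS is the SPD primary, its secondary listing reuses primary data.

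**Working it through.** **Inputs from the documents.** Standardized effect 0.5, 80% power, two-group t test at .05, 50 per group (Sample Size); 50 participants in total at 1:1, so 25 per arm (Methodology). Scale ranges, SDs, mean changes and the TTM:SPD mix are not given.

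**The plan's own figure.** In the normal approximation, n per arm = 2(z_α + z_β)²/d².

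- One-sided: 2(1.645 + 0.842)²/0.25 = 49.5, so 50. The t test gives 50.15, so 51.
- Two-sided: 2(1.960 + 0.842)²/0.25 = 62.8, so 63. The t test gives 63.8, so 64.

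The stated 50 per group therefore matches a one-sided test; the plan does not state the sidedness. At 25 per arm, t-test power for d = 0.5 is 41% two-sided (54% one-sided). The 41% is the reference below. The gap between 50 per group and 50 in total is a separate matter.

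**Effect of raw pooling.** Let p be the share with SPD, k the ratio of change SDs (SPD to TTM), and m the difference between diagnoses in mean change, in TTM SD units. With a true effect of 0.5 SD within each diagnosis:

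- pooled difference D = 0.5[(1 − p) + pk]
- pooled variance V = (1 − p) + pk² + p(1 − p)m²
- effective size = D/√V
- SPD share of the estimate = pk/[(1 − p) + pk]

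With p = 0.5, 25 per arm and a two-sided test:

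| k | m | D/√V | Effective size | Power |
|---|---|---|---|---|
| 1 | 0 | 0.50/√1.00 | 0.50 | 41% |
| 2 | 0 | 0.75/√2.50 | 0.474 | 38% |
| 1 | 1 | 0.50/√1.25 | 0.447 | 34% |
| 2 | 1 | 0.75/√2.75 | 0.452 | 35% |
| 2 | 2 | 0.75/√3.50 | 0.401 | 28% |

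At k = 2, SPD carries 1/1.5 = 67% of the estimate with 50% of the participants. When k differs from 1, the gap between diagnoses in the active arm is m + 0.5k − 0.5 rather than m. Averaging the variance over the two arms on that basis lowers the three k = 2 rows to 37%, 33% and 27%. Milder ratios cost little: at m = 0, k = 1.5 gives 40%.

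**Chance imbalance.** With 25 SPD participants among 50 and allocation that ignores diagnosis, the between-arm difference in SPD share has an SD of 14 percentage points. A difference of 20 points or more occurs in 26% of allocations. With no drug effect, the shift in the estimate is imbalance × m, for example 0.20 × 1 = 0.20 TTM SD units. It is zero when m = 0.

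**Simulation** (6,000 runs per scenario, 25 per arm, p = 0.5; k, m = 1, 0; 1, 1; 1.5, 1; 2, 1; 2, 2). Raw pooling gave power of 41%, 34%, 34%, 33% and 27%. Change standardized within diagnosis, with a diagnosis term, gave 39.5% to 40.6% throughout. With no drug effect, rejection rates were 4.8% to 5.4% across both analyses.

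**The case against.** The strongest objection is that the analysis text may already use one parent scale. Primary endpoint analysis names only the NIMH scale, in a plural that fits the original and its skin-picking modification. Baseline Assessments agrees, and the SP-SAS appears as a secondary self-report. On that reading there is a nominal common unit, and the mismatch in rater mode does not arise. This stands. A reader might infer from the first clause of the co-primary definition that the SP-SAS is the SPD primary and that the estimate certainly has no common unit; the documents contradict themselves and do not settle that. What remains is that equivalence of the two NIMH versions is not shown, and a difference in mean change would still go unmodelled.

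A reader might also infer that the pooled test is biased or invalid. It is not: randomization balances diagnosis in expectation, and simulated type I error stays near 5%. Nor is it established that one diagnosis dominates or that case mix adds noise. The first needs unequal SDs, the second unequal mean changes or SDs. The opposite inference, that equal SDs make pooling harmless, also fails when mean changes differ, as the row k = 1, m = 1 shows.

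Finally, pooling is a declared choice in a self-described pilot, with a rationale in Background (shared neurobiology and response to the same interventions). That supports enrolling and analysing both diagnoses together. It does not argue against a diagnosis term.

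**Conclusion.** The concern holds as one of interpretability and precision, for the symptom co-primary only. The Sheehan Disability Scale, read as a separate co-primary as in Co-Primary Endpoint(s), is common to both diagnoses and is unaffected.

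If the SP-SAS is the SPD primary, the raw pooled difference has no common unit. If the modified NIMH scale is, the unit is nominally common but unverified. The loss of power, from 41% to between about 38% and 28% in the three cases given in the summary, depends wholly on assumed values of k, m and p and a true effect of 0.5 in each diagnosis. It is nil when SDs and mean changes are equal. The documents cannot show where the trial lies in that range. The change is still worth making, because in simulation the adjusted analysis held about 40% power in every scenario, and a diagnosis term helps under either reading of the instrument.

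**What to change.** 1. In Co-Primary Endpoint(s), Baseline Assessments, Primary endpoint analysis and Secondary endpoints analyses, name the same primary symptom scale and rater mode for SPD. Do not list that scale again as secondary, there or under Secondary Endpoint(s).
2. In Primary endpoint analysis, add diagnosis (TTM or SPD) as a term in the model.
3. If the two diagnoses keep different instruments, divide each participant's change by the baseline SD of the relevant scale within diagnosis before pooling. Using one parent scale for both would avoid this step, but the diagnosis term should stay. The simulation above standardized by the SD of change; baseline SDs equalize the spread only as far as the ratio of change SD to baseline SD is similar in the two diagnoses.
4. Report the treatment effect on each raw scale by diagnosis.
5. For participants with both disorders, record the index behaviour, and so the primary scale, before randomization.

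The cost is wording in the protocol and analysis plan and one degree of freedom. Where scores are standardized, the headline effect is in SD units, which the by-diagnosis raw results offset. The rule should be fixed before unblinding, so that the choice of pooling method cannot depend on the result.
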